4. SELECTION OF PARTICIPANTS

Adult women aged 21 or older with bothersome MUI (defined as bothersome SUI and UUI) will be eligible.

4.1 Eligibility Criteria/Rationale for Inclusion/Exclusion

4.1.1 Defining the MUSA MUI Population

The MUSA population consists of women with bothersome MUI. Women in MUSA must report subjectively bothersome SUI and UUI and must also objectively demonstrate SUI and UUI. In determining eligibility criteria, the protocol committee considered the ultimate goal of MUSA. The population of MUSA are women with MUI who would benefit from either Botox A or mid-urethral sling but it is unclear whether treatment should begin with Botox A or mid-urethral sling. Therefore, participants must have bothersome

symptoms, however, criteria are not so strict that women on either the moderate or severe end of the spectrum are excluded or recruitment is hindered (as was in MIMOSA).

A single instrument that provides objective documentation of both SUI and UUI does not exist. A bladder diary allows documentation of both conditions; however, women are frequently unable to clearly characterize a leakage episode as SUI or UUI. Similarly, more invasive UDE testing also allows objective documentation of SUI and detrusor overactivity (DO) but DO correlates poorly with OAB symptoms and UDE does not predict treatment outcomes of either SUI or UUI.⁹⁰⁻⁹³ Therefore, similar to ESTEEM, MUSA will use a variety of instruments to identify women with MUI who have both subjective and objective evidence of MUI. This includes subjective documentation of at least moderately bothersome SUI and UUI on a PRO (UDI), objective documentation of UUI on bladder diary, and objective documentation of SUI by CST or UDE.

Rationale for Bladder diary criteria for MUSA

In determining the number of episodes required on bladder diary for inclusion into MUSA, the protocol committee reviewed bladder diary criteria for existing SUI and UUI trials (see tables 1 and 2 on Botox and mid-urethral sling). SUI trials typically have not used a bladder diary inclusion criterion; objective criteria of SUI is met by CST or UDE. Most Botox A trials have specified the number of UUI episodes in their inclusion criteria. The ESTEEM trial has shown that worse OAB (DO on urodynamics, previous OAB medication use, and for the sling only group, higher baseline UDI irritative subscore) is a predictor of failure to treatment, based on combined subjective (not meeting MCID for UDI-total score) and objective (not achieving >70% improvement on mean IE/day or additional SUI / UUI treatment) criteria. The team decided that at least 4 UUI episodes on a 3-day diary would be appropriate for documenting objective UUI and allow recruitment of a MUI population with higher UUI bother than ESTEEM while not necessarily being UUI-predominant. In ESTEEM, 70% of participants at baseline had at least 4 UUIE in 3 days (≥ 1.3 UUIE/day on average); this population had a mean 3.7 UUIE/day, 2.5 SUIE/day, 6.6 total UIE/day, 70 UDI-irritative score, and 85 UDI-stress score and an overall 20% failure rate at 3 months. The number of UUI incontinence episodes has purposefully not been set as high as previous Botox trials (Table 1) because the MUSA population is not limited to a refractory UUI or UUI-predominant population and to allow recruitment of a broad spectrum of women with MUI. Additionally, MUSA's primary outcome is not defined by diary improvement.

Rationale for Urodynamic evaluation inclusion criteria for MUSA

The protocol committee considered the utility of including UDE as a MUSA inclusion criteria. Given that this is the first trial to compare treatment with Botox A versus mid-urethral sling in women with MUI, baseline UDE information was considered important. In addition, other studies in women with MUI undergoing mid-urethral sling surgery have reported association of baseline UDE parameters with treatment failure. Paick et al reported that low maximal urethral pressure at baseline UDE was associated with a greater risk of persistent OAB after mid-urethral sling²³. In ESTEEM, baseline UDE parameters that predicted failure included detrusor overactivity, lower volume at first urge, and Valsalva leak point pressure <60 cmH₂O. Thus, standardized UDE will be performed before study interventions.

There are no specific UDE parameters that determine eligibility for this trial beyond diagnosis of SUI defined by a positive CST or UDE. Patients in MUSA will undergo UDE testing, primarily to allow evaluation of variables that may predict clinical outcome. If patients have already undergone UDE prior to enrollment, results performed within 18 months of enrollment will be allowed if studies meet MUSA

standards. MUSA will use UDE standards similar to ESTEEM. For those women who have not had UDE in the past 18 months, UDE will be performed before randomization.

4.1.2 Targeting a Population That is Distinct From ESTEEM

While several inclusion criteria of MUSA are similar to that of the recently completed ESTEEM study, there are also important differences. First, inclusion criteria for the number of UUIE per day is higher in MUSA than ESTEEM, thus ensuring recruitment of a population with higher UUI bother (see above *Defining the MUSA MUI Population*). Second, unlike ESTEEM, desire for surgical treatment for SUI symptoms is not an inclusion criterion for MUSA. Removing this criterion ensures that participants are eligible for both Botox A and mid-urethral sling. Additionally, removing this criterion prevents unconscious bias of including a stress-predominant MUI population in MUSA.

Behavioral therapy is first line management for urinary incontinence, either stress or urgency UI. In MUSA, women must report persistent symptoms despite at least one or more conservative treatments, (e.g. supervised behavioral/physical therapy).

After extensive discussion, the protocol committee ultimately decided that “failure” (inadequate response, intolerant of, or for whom they are contraindicated as determined by the physician) of medical therapy with anti-cholinergic and/or beta-mimetic medications would be an eligibility criterion per Botox label indications.

Based on the above rationale, the MUSA inclusion/exclusion criteria are as follows:

4.2 Inclusion Criteria

1. Reporting at least “moderate bother” from UUI item on UDI
 - a. “Do you experience urine leakage associated with a feeling of urgency?”
2. Reporting at least “moderate bother” from SUI item on UDI
 - a. “Do you experience urine leakage related to physical activity, coughing, or sneezing”
3. Diagnosis of SUI defined by a positive cough stress test (CST) or UDE within the past 18 months
If participant does not demonstrate SUI during CMG they must demonstrate SUI through a cough stress test or other comparable valsalva maneuver to be eligible.
4. Presence of UUI on bladder diary with ≥ 4 Urgency IE/3-day diary
5. Urinary symptoms ≥ 3 months
6. Persistent symptoms despite at least one or more conservative treatments (e.g. supervised behavioral therapy, physical therapy) as determined adequate by the physician.
7. Inadequate response to oral overactive bladder medications (including anti-cholinergic and/or beta-mimetic medication) unless patient is
 - a. intolerant of oral overactive bladder medications, or
 - b. oral overactive bladder medications are contraindicated as determined by the treating provider.
8. Urodynamics within past 18 months prior to enrollment or done after enrollment, prior to randomization.

9. Demonstrates understanding (or have caregiver demonstrate understanding) to perform clean intermittent self-catheterization.
Provider and patient review CISC process and patient (and/or caregiver) demonstrates understanding to the satisfaction of the provider.

4.3 Exclusion Criteria

1. Anterior or apical compartment prolapse at or beyond the hymen (≥ 0 on POPQ), regardless if patient is symptomatic
 - a. Women with anterior or apical prolapse above the hymen (<0) who do not report vaginal bulge symptoms will be eligible
2. Planned concomitant surgery for anterior vaginal wall or apical prolapse ≥ 0
 - b. Women undergoing only rectocele repair or other repair unrelated to anterior or apical compartment are eligible
3. Women undergoing hysterectomy for any indication will be excluded
4. Active pelvic organ malignancy
5. Age <21 years
6. Pregnant or plans for future pregnancy in next 6 months, or within 12 months post-partum
7. Post-void residual >150 cc on 2 occasions within the past 6 months, or current catheter use
8. Participation in other trial that may influence results of this study
9. Unevaluated hematuria
10. Prior sling, synthetic mesh for prolapse, implanted nerve stimulator for urinary incontinence
Women with known Burch or Marshall-Marchetti-Krantz (MMK) are excluded.
11. Spinal cord injury or advanced/severe neurologic conditions including Multiple Sclerosis, Parkinsons, Myasthenia Gravis, Charcot-Marie-Tooth
12. Women on overactive bladder medication/therapy will be eligible after 3 week wash-out period
13. Non-ambulatory
14. History of serious adverse reaction to synthetic mesh
15. Not able to complete study assessments per clinician judgment, or not available for 6 month follow-up
16. Diagnosis of and/or history of bladder pain or chronic pelvic pain
17. Women who had intravesical Botox injection within the past 12 months
18. Women who have undergone anterior or apical pelvic organ prolapse repair within the past 6 months

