4.4 Screening for Eligibility

It is anticipated that participants will be recruited from PFDN Clinical Site practices. Women with MUI will be offered the full range of treatment options consistent with routine practice including expectant management, pelvic floor muscle therapy, behavioral therapy, medication, and possibly surgery. Patients who are considered candidates for either Botox A injection or mid-urethral sling by their physician will be offered participation in MUSA.

Subjects will be identified as MUSA candidates by their physician. Subjects will be approached by study personnel consistent with local IRB requirements. Enrollment will occur after written and/or verbal consent. If the participant accepts participation in MUSA, the UDI will be administered to confirm at least moderate bother from both SUI and UUI and the coordinator will confirm documentation of SUI by either CST or UDE within the past 18 months, and UI symptoms for at least 3 months. She will be instructed on how to complete the voiding diary.

To address the issue of overactive bladder medication use, these subjects will be required to have a washout of 3 weeks prior to completing the voiding diary. The anticholinergic medication with the longest half-life currently on the market is Vesicare with a half-life of 45-68 hours. Therefore, by 1 week there should be negligible amounts in the bloodstream and by 2 weeks the drug would be completely out of the system. Therefore, 3 weeks should be adequate time for washout and this time period is consistent with prior PFDN studies (ABC trial,³⁵ ESTEEM,⁴⁹ ROSETTA³³). In addition, because we are highly interested in what happens to OAB outcomes, subjects will need to remain off overactive bladder medication for the 6 month duration of the study to allow accurate assessment of these symptoms following treatment (See statistical analysis plan for details). Subjects who take overactive bladder medication during the study period will be considered as having “additional treatment”. Every effort will be made to schedule the patient’s surgery within 2 months from enrollment (see Section 4.6, Appointment scheduling below).

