To address the issue of surgeon certification for Botox intradetrusor injection and to ensure standardized training of all surgeons, all “certified surgeons” administering injections will be required to view a short instructional video demonstrating optimal techniques and detailing sites of drug injection in a standardized manner. In addition, “certified surgeons” at each site must have previously performed a total of 10 intradetrusor injection procedures.

5.2.2 *Standardization of Botox Injection Procedures*

Detailed standardization of the surgical procedure will be developed and will include the following key points:

1. The Coordinator will ensure that the subject has been instructed regarding the proper technique for clean intermittent self-catheterization (CISC) and will confirm that the subject or designated caretaker is able to perform the task.

2. Within one week prior to injection, a confirming urine pregnancy test will be performed in all premenopausal women. A urine dip to rule out infection will also be performed. If the urine dip is positive the participant will be treated for a urinary tract infection and rescheduled within 4 weeks for Botox A® injection visit.
3. The bladder will be catheterized and 50 ml of 2% lidocaine placed in the bladder and 10 ml of 2% lidocaine jelly in the urethra. The subject will be asked to lie on their left and right lateral decubitus for several minutes at a time to ensure diffuse anesthetic effect on the bladder. Cystoscopic surveillance of the bladder will be used to confirm normality.

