4. Cystoscopy will be performed with a 12 or 30-degree lens and rigid or flexible scope. A 22 gauge disposable needle, which is passed through the cystoscopic channel, will be used. Approximately 100-200 ml of total fluid will be instilled during cystoscopy to allow adequate visualization of the entire bladder urothelium. Botulinum toxin A will be prepared by dissolving 100 units of botulinum toxin A into 10 ml of injectable saline. Indigo carmine or methylene blue 0.1 ml will be added to each syringe of botulinum toxin A. The treating physician will inject a total of 10 ml of the Botox A® into approximately 15 to 20 different detrusor muscle sites under direct visualization. Injections will be spread out to equally cover the posterior bladder wall and dome, but spare the bladder trigone and ureteral orifices. The anterior bladder dome will be not be injected secondary to technical difficulties associated with injecting this area cystoscopically.
5. The Coordinator will record peri-procedural events and complications. The instilled fluid will be left in the bladder after the injections are complete. The subject will remain in a post-procedure area until a spontaneous void occurs. The patient must have a spontaneous void before going home. All subjects will receive a single dose of antibiotics orally per standard of care immediately after injection and subjects will take antibiotics orally once daily for 3 days post injection.

5.2.3 *Criteria for Botox Reinjections*

Participants with persistent bothersome UUI at 3 months after their initial 100 unit Botox A injection may receive one additional injection of 100 units Botox A between 3 months and 6 months after initial injection. Eligibility for repeat Botox A injection are:

1. Persistent bothersome UUI as determined by reporting at least “moderate bother” from UUI item on UDI: “Do you experience urine leakage associated with a feeling of urgency, that is a strong sensation of needing to go to the bathroom?”
2. Continued UI bother based on the Patient Global Symptom Control (PGSC): “My current treatment is giving me adequate control of my urinary leakage”, score of ≤ 3
3. Participant desires additional treatment with Botox A
4. No UTI as determined by the health care provider on the day of the PGSC evaluation
5. PVR < 200 ml, per Botox A guidelines for UUI
6. No medical contraindication for the procedure as determined by the physician

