7. Continuing to meet study inclusion/exclusion criteria (except inclusion items 2, 3, 4 7 and 8 and exclusion item 7).

A maximum of 1 additional 100 unit Botox A injection will be allowed between 3 and 6 months (total of 2 injections of 100 units Botox A). No injections will be given at an interval less than 3 months and the participant will have a post injection visit at 2 weeks (+/- 1 week) following injection.

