5.3.2 Postoperative Visits and Procedures

Patients will undergo clinical and PRO assessments at 2-weeks, 3 months, and 6 months postoperatively (See **Table 9**). The primary outcome will be at 6 months.

Table 9: Timeline of Visits, Events, and Data Collection

	Screening	Baseline	Procedure (Botox or Sling) ^{‡, **}	1-2 Week Visit ^{**}	Telephone Call	3 Month Visit	Botox reinjection ^{‡, **}	1-2 Week Visit ^{**}	Telephone Call	6 Month Visit [†]
Window	1-4 w	1-4 w			1w before 3m visit	2 w pre – 4 w post			1w before 6m visit	2 w pre – 4 w post
Consent	X									
Coordinator visit	X	X		X	X	X		X	X	X
Hx/PE	X	X				X				X
Urodynamics**		X								
Medication and other treatment audit	X	X				X				X
Preg test~**			X				X			
Urine dip~**	X	X	X	X		X	X	X		X
PVR	X	X		X		X		X		X
Adverse Events			X	X		X	X	X		X
PGSC						X				X
UDI		X				X				X
Bladder diary		X			Diary reminder	X			Diary reminder	X
PRO/Questionnaires Varies by milestone.		X		X		X		X		X

[†] primary outcome visit

* all subjects will undergo a post-op visit for PVR/urine dip 2 weeks after Botox A or sling procedure

[‡] standard of care visit

** must be done in clinic

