7.5.3 Botox A Contraindications¹⁰²

BOTOX is contraindicated in patients who are hypersensitive to any botulinum toxin product or to any of the components in the formulation. In the presence of infection at the proposed injection site(s). For intradetrusor injection in patients with a urinary tract infection; or in patients with urinary retention or post-void residual (PVR) urine volume >200 mL who are not routinely performing clean intermittent self-catheterization (CIC).

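### Exclusion 7 needs two high residuals, so a woman whose only high post-void residual is her latest one, above 200 mL, can be randomised although section 7.5.3 lists Botox as contraindicated for her

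*Protocol*

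**What the plan says.** - **Entry.** Protocol 4.3 item 7, with the same wording in SAP 4.2, excludes for "Post-void residual >150 cc on 2 occasions within the past 6 months, or current catheter use".
- **Contraindication.** Protocol 7.5.3 covers urinary tract infection, urinary retention, and a "post-void residual (PVR) urine volume >200 mL who are not routinely performing clean intermittent self-catheterization". Inclusion 9 asks only that the woman or a caregiver understands self-catheterisation.
- **First injection.** Protocol 5.2.2 opens with "Detailed standardization of the surgical procedure will be developed and will include the following key points". The checks listed before injection are self-catheterisation readiness, where the coordinator "will confirm that the subject or designated caretaker is able to perform the task", a pregnancy test and a urine dip. No residual limit is listed.
- **Reinjection.** Protocol 5.2.3 item 5 requires "PVR < 200 ml, per Botox A guidelines for UUI", item 6 requires that the physician finds no medical contraindication, and item 7 waives exclusion 7.
- **Candidacy.** Protocol 4.4: "Patients who are considered candidates for either Botox A injection or mid-urethral sling by their physician will be offered participation in MUSA". It gives no residual limit.
- **Schedule.** In Protocol 5.3.2, "Table 9: Timeline of Visits, Events, and Data Collection" marks the residual at screening and baseline, and at neither injection visit. The SAP 4.6 grid, as extracted, marks it at baseline and at reinjection, but not at screening, repeat baseline or the first procedure.

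**The concern.** The entry rule and the contraindication use different tests. Exclusion 7 has the lower threshold but needs two readings above it. Section 7.5.3 has the higher threshold and no such requirement. A woman can therefore pass the first and fail the second. The exception in 7.5.3 for routine self-catheterisation is closed to her, because exclusion 7 also bars current catheter use.

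Section 5.2.2 turns one of the bladder contraindications, infection, into a written stop before injection: dip, treat, reschedule. It does nothing comparable for the residual. For reinjection the protocol writes down both a residual limit and a contraindication check.

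Two outcomes are possible for such a woman in the Botox arm. She may be injected in a state the protocol lists as contraindicated. Or the surgeon may decline after randomisation, a decision with no counterpart in the sling arm. If she then never receives study treatment, she leaves the modified intention-to-treat population (Protocol 6.2.1, SAP 5.1), while a similar woman allocated to sling stays in. Both outcomes can be avoided with a measurement that is already scheduled at baseline.

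**Working it through.** No power or sample-size figure bears on this point. The check applies the two rules to example readings (cc and mL are the same unit).

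**Inputs**
- Exclusion 7: at least two readings >150 within 6 months (Protocol 4.3).
- Contraindication: most recent reading >200, woman not self-catheterising (Protocol 7.5.3; current catheter users are already excluded).
- Conflict: not excluded by item 7, but contraindicated.

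| Readings, oldest first | Number >150 | Excluded by item 7 | Latest >200 | Conflict |
|---|---|---|---|---|
| 140, 250 | 1 | no | yes | **yes** |
| 120, 210 | 1 | no | yes | **yes** |
| 250 only | 1 | no | yes | **yes** |
| 160, 210 | 2 | yes | yes | no |
| 210, 220 | 2 | yes | yes | no |
| 210, 100 | 1 | no | no | no |
| 120, 190 | 1 | no | no | no |

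The conflict needs the latest reading to be above 200 mL and every other reading in the 6 months to be at or below 150, or absent.

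**Which schedule applies.** Under Protocol Table 9 every woman has two readings, so one who is persistently above 200 mL is excluded and only the discordant case remains. Under the SAP grid there is one scheduled reading. The row with 250 alone is then possible unless the chart supplies a second value.

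**Effect of the proposed clause** (latest reading >200 mL not eligible; one repeat allowed, whose value decides this clause). All three conflict rows are stopped before randomisation, and the rows 210, 100 and 120, 190 are unaffected. For the woman with 140 then 250:
- Repeat 120: eligible.
- Repeat 170: she passes the new clause. If the repeat counts as a second occasion, 250 and 170 are both above 150 and item 7 itself excludes her.
- Repeat 210: excluded by the new clause, and by item 7 if the repeat counts.

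If the repeat counts as an occasion, the clause excludes nobody after a repeat whom item 7 would not also exclude. Its main work is to prompt the second reading.

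**The case against.** The strongest reply is that the matter is handled elsewhere. Section 7.5.3 is protocol text and covers every injection. Section 4.4 offers the trial to women their physician thinks suitable. Section 5.2.2 lists key points only, so a residual check may sit in the fuller procedure. Item 3 of 5.2.2 also catheterises the bladder just before injection, when a large residual could be noticed. The reinjection limit can be read as a substitute for the waived exclusion 7, not as evidence of an oversight. And requiring two occasions is a sensible guard against one spurious reading.

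Much of this stands. The two-occasion rule should stay, and absence from a list of key points is weak evidence of absence from practice. But candidacy under 4.4 is judged before the baseline residual and carries no figure. Catheterisation in item 3 is not a stated residual test. Reliance on 7.5.3 on the day puts the decision after randomisation and in one arm.

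A reader might infer more than the documents support:
- **That women with persistently high residuals are enrolled.** Under Table 9 they have two readings above 150 and are excluded.
- **That her infection risk is known.** Protocol 7.5.5 reports urinary tract infection in 44% versus 23% by maximum residual *after* injection, which does not measure the risk of a woman with one high reading before it.
- **That she would distort the retention outcome.** The >200 mL level in SAP 9.2 triggers a query for unreported adverse events, which are counted from randomisation. A baseline reading is not such an event.
- **That the protocol's visit schedule checks the residual at reinjection only.** Protocol Table 9 marks it at neither injection visit; only the SAP grid marks it at reinjection. The firm contrast is the written criterion in 5.2.3.

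**Conclusion.** The gap is real on the text. A woman whose only high residual is her latest, above 200 mL, meets the entry criteria, while Botox is listed as contraindicated for her. No other item in 4.2 or 4.3 catches her.

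It is a narrow gap. The documents give no distribution of residuals at entry, so the number affected cannot be estimated; it is probably small. They do not show that any such woman would in fact be injected, and no effect on the primary result is claimed. The conclusion assumes she has no other reading above 150 cc in the past 6 months, and that no residual limit for the first injection exists in a procedure outside these documents. If one does, citing it would meet most of the point. What would remain is that the decision falls after randomisation.

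The priority is optional to modest. This is a cheap safety clarification, not a major defect.

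**What to change.** 1. **Protocol 4.3 and SAP 4.2.** Keep exclusion 7 and add, for both arms before randomisation: *or most recent post-void residual >200 mL (may be repeated once to confirm; the repeat value decides)*. State that the repeat decides this clause only, and whether it counts as an occasion for exclusion 7. The >200 limit matches 7.5.3; the reinjection rule differs only at exactly 200 mL.
2. **Protocol 5.2.2.** Before the first injection, cross-refer to the 7.5.3 limit as a safety backstop, using the latest available residual. A woman who is deferred stays in follow-up under Protocol 4.6.
3. **Schedules.** Mark the residual in the repeat-baseline column. SAP 4.3 says baseline assessments are repeated when treatment is not completed within 91 days of the baseline UDI, but the grid does not mark the residual there. Where that repeat falls after randomisation, the value serves the backstop in 5.2.2. Align the SAP grid with Protocol Table 9 on the screening reading.

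The cost is amendment wording, an occasional repeat residual, and a few women excluded from both arms, including the sling arm, on a limit specific to Botox. The sample size is unchanged. SAP 7.7 describes enrolling sites in the past tense. If recruitment has closed, the useful step is to report how many Botox-arm women had a last pre-treatment residual above 200 mL.
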